5.5 Drug circuit

5.5.1 Supply

Protopic® 0.1% tubes are ordered by the subcontractor: Unither pharmaceuticals, to carry out the blinding operation.

For the manufacture of the placebo, all operations are managed by the subcontractor: Unither pharmaceuticals, supply of raw materials, manufacturing, filling, masking, and analytic control.

Tubes of Protopic® and placebo are sent to the Central Pharmacy at the Hospices Civils de Lyon. They will be labeled, released and stored on their premises.

The pharmacies in the centers participating in the study are supplied by the Central Pharmacy at the Hospices Civils de Lyon.

5.5.2 Dispensing the study products by the hospital pharmacy in the centers participating in the study

The doctor investigator prescribes Protopic® 0.1% or placebo on the specific prescription sheet for the study. The information provided by the doctor will be:

- date of the prescription;
- surname, forenames and date of birth of the patient using a patient sticker;

- The patient's identification number.
- The treatment code.

The original of the prescription will be taken to the hospital pharmacy of the Hospital Center. The product allocated is then dispensed.

Before delivery, the tube is weighed. It will be weighed again after its return to calculate the total quantity administered. These data processed by the pharmacies will be available if necessary.

One tube is delivered to each patient; a specific leaflet is included with recommendations and application modalities.

All the traceability of the treatments used will be consigned to the prescription register specific to the trial at the HOSPITAL PHARMACY at the Hospital Center.

5.6 Ointment tubes: presentation and supplier

The primary packaging is a laminate tube with an inner lining of low-density-polyethylene fitted with a polypropylene screw cap.

Protopic® 0.1% is manufactured by Astellas pharma.

The placebo formulation is manufactured by Unither Pharmaceuticals.

6 Practical running of the study

6.1 General organization and study sites

Patients will be recruited and informed during a standard consultation with the ENT doctor or doctor responsible in the reference center or skill center for HHT. Patients will be informed of the study and the need to complete nosebleed grids for ENT monitoring for the 6 weeks prior to the start of the treatment (Appendix 1: Nosebleed monitoring grid, a grid completed daily by patients).

The inclusion of the patients will take place when they come for a consultation for prescription of the treatment.

The treatment will be self-administered by the patient, twice daily, for 6 weeks.

Two follow-up visits are organized, at the end of the 6 weeks of treatment, and 6 weeks after the end of the treatment, with medical consultations in the department responsible for coordinating HHT (Reference or skill center) and in the ENT department of each center.

FK-506 dosage in blood are scheduled on Day 8, 22 and 43.

A phone call is scheduled on day 15 and 31 (i.e. 14 and 30 days after the beginning of the treatment) in order to collect information regarding tolerance and observance.

[figure not shown]

Figure 8: Diagram of the running of the study

6.2 Inclusion visit (V1)

Patients will be seen at a consultation for the treatment by a doctor and a clinical research assistant from the center if possible.

At this visit:

- The investigator will once again inform the patients about the study.
- The nosebleed grids completed by the patient in the 6 weeks prior to the treatment will be collected (Appendix 1: Nosebleed monitoring grid).
- The inclusion and exclusion criteria will be verified and the consent form will be signed. The investigator connects to the platform, includes the patient and an identification number will be assigned to the patient.
- The patient will undergo a clinical examination, including blood pressure and heart rate.
- A urinary pregnancy test will be performed for all female patients of child-bearing age. The investigator will inform these patients that there is no data available in pregnant women and they must use an effective contraceptive method (combined hormonal contraceptive, implant, intra-uterine device). The use of any other means, such as condom, will be left to the judgment of the investigator; the patient will have to give her commitment which will be recorded in the medical file.
- The number of red blood cell transfusions in the 6 weeks prior to administration of the treatment will be noted (as noted by the patient on the nosebleed grids).
- Any concomitant treatments will be noted.

If all the criteria are validated:

- The examination will be completed by a set of biological blood samples (2 x 5 mL tubes) for hemoglobinemia and serum ferritin.

- An ENT examination will be carried out (Appendix 3: Monitoring ENT examination).
- The ESS questionnaire is completed by patient (Appendix 2).
- An SF36 quality of life questionnaire will be given to the patient for completion.
- The nosebleed grids will be given to the patient for ENT monitoring during the 6 weeks of treatment (Appendix 1: Nosebleed monitoring grid). Specific boxes are provided to mark the two daily administrations, in order to verify observance of the treatment. If convenient for the patient a connexion code can be provided to allow them to complete these grids online on eCRF.
- Drug dispensation: The prescription for the drug will be made, and the product will be delivered by the pharmacist at the hospital. Patients are carefully instructed how to apply the medication through an in vivo demonstration and a written description is provided with the product in which the modalities of application are reported.
- A clinical trial participation card will be given to the patient. It will include phone numbers if needed and in case of emergency. Recommendations are given in case of the onset adverse events.
- A specific prescription will be given to the patient for the dosage of FK506 in blood, one week and three weeks after the beginning of the treatment (i.e. on Day 8 and Day 22). Blood sample will be taken in a laboratory selected by the patient; the latter will send the tube in the biological laboratory for a centralized analysis.

If the criteria are not validated, the patient may be asked to return at a later date if the inclusion criteria can be normalized.

6.2.1 Ointment administration

The ointment is self-administered by the patient twice daily.

About 0.1 g of product should be administered in each nostril. The tube is gently squeezed to extract an amount roughly equivalent to the size of the head of a cotton swab.

The ointment is introduced into each nostril with a finger or a cotton swab. Patients can choose the most convenient way for them to administer the product. The product is extended inside the nostril with a cotton swab or/and by external pressure on the nostril.

Should other nasal product be used, such as physiologic serum or gelositin for example, we recommend that the other product not be applied simultaneously but at a different time, for example two hours before or after the tested product.

6.2.2 Recommendations

Patients will receive recommendations on how to contact the doctor in case of the onset of adverse events.

A burning sensation is frequently observed at the administration site; usually this sensation is acceptable and disappears after a few days of administration.

In case of an adverse event probably due to the product: skin irritation, an unacceptable burning sensation, pruritus, and erythema, at the application site:

- The patient must stop the treatment.
- He or she must inform the investigator as soon as possible.
- Based on symptoms, a medical consultation can be carried out by a general practitioner, a specialist or an investigator involved in the study.
- The treatment can be reintroduced, or not, after clinical normalization.
- It is up to the investigator to make the decision in the interest of the patient, on the basis of the balance between the risk of a new event and the risk of aggravation of the disease.

The modalities for managing nosebleeds will be given to the patients to inform all doctors of the treatment of the nosebleeds specific to this disease.

6.3 Phone calls on day 15, 14 days after the beginning of the treatment (up to day 18 tolerated)

Patients will be contacted by phone, 14 days after the beginning of the treatment, to collect intermediate data regarding tolerance and observance.

The following data will be collected:

- Treatment observance: any interruption to the treatment interruption will be noted precisely (date, duration), as will the reason for the interruption.
- Occurrence of adverse events: nature, date of onset, and whether or not a symptomatic treatment was given.
- Any change in the concomitant treatments.
- The date of the blood sample planned at day 8 (FK506 dosage).

6.4 Phone calls on day 31, 30 days after the beginning of the treatment (up to day 37 tolerated)

Patients will be contacted by phone, 30 days after the beginning of the treatment, to collect intermediate data regarding tolerance and observance.

The following data will be collected:

- Treatment observance: any interruption to the treatment interruption will be noted precisely (date, duration), as will the reason for the interruption.
- Occurrence of adverse events: nature, date of onset, and whether or not a symptomatic treatment was given.
- Any change in the concomitant treatments.
- The date of the blood sample planned at day 22 (FK506 dosage).

6.5 Visit at the end of the treatment, V2 = at day 43 (up to day 50 tolerated)

The patients will be seen in consultation, in the Reference center or skill center for HHT.

The following examinations/consultations will take place:

- Clinical examination including blood pressure and heart rate.
- Collection of the nosebleed grids completed by the patients during the 6 weeks of treatment (Appendix 1: Nosebleed monitoring grid), if not completed on line. These grids include monitoring of treatment administrations.
- The ESS questionnaire is completed by patient (Appendix 2).
- New nosebleed grids will be given to the patients for ENT monitoring during the next 6 weeks (Appendix 1: Nosebleed monitoring grid), if not completed online.
- The number of red blood cell transfusions received by the patient in the last 6 weeks will be noted.
- Patients will return the product, it will be transmitted to the hospital pharmacy.
- A set of biological blood samples (2 x 5 mL tubes) is collected: hemoglobinemia and serum ferritin.
- A blood sample is collected (4 mL on EDTA) for tacrolimus dosage.
- An SF36 quality of life questionnaire will be given to patients for completion.
- Monitoring and collection of any adverse events.
- Concomitant treatments will be noted.

6.6 Visit after 6 weeks follow-up, V3 = at day 85 (up to day 100 tolerated)

The patients will be seen in consultation, in the Reference center or skill center for HHT.

The following examinations/consultations will take place:

- Clinical examination including blood pressure and heart rate.
- Collection of the nosebleed grids completed by the patients during the 6 weeks' follow-up after the treatment (Appendix 1: Nosebleed monitoring grid), if not completed online.
- The ESS questionnaire is completed by the patient (Appendix 2).
- The number of red blood cell transfusions received by the patient in the last 6 weeks will be noted (as noted by the patient on the nosebleed grids).
- A set of biological blood samples (2 x 5 mL tubes) is collected: hemoglobinemia and serum ferritin.
- An SF36 quality of life questionnaire will be given to patients for completion.
- Monitoring and collection of any adverse events.

- Concomitant treatments will be noted.

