1.3.4 Pharmacokinetic and systemic absorption

Data from healthy human subjects indicate that there is little or no systemic exposure to tacrolimus following repeated topical application of tacrolimus ointment. As systemic exposure is low with tacrolimus ointment, the high binding of tacrolimus to plasma proteins is not considered to be clinically relevant. The metabolism of tacrolimus by human skin was not detectable. Systemically-available tacrolimus is extensively metabolized in the liver via CYP3A4. Following repeated topical application of the ointment, the average half-life of tacrolimus was estimated to be 75 hours for adults and 65 hours for children.³⁶

Several studies in infants^{55,56} on the pharmacokinetics of tacrolimus after first and repeated application showed minimal systemic exposure. 92% of blood samples contained tacrolimus concentrations of less than 1 ng per mL and 17% of samples were less than 0.025 ng per mL (lower limit of quantification). These values are minimal compared with an oral dose after a liver transplant. Systemic exposure to tacrolimus increased in proportion to the size of the body surface treated, and decreased with time as the skin lesions healed. There was no evidence of systemic accumulation.

Further to an administration on mucosae, pharmacokinetic was evaluated in two clinical trials and no systemic absorption was detected^{47,49}.

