- ≥ 4 patients in both arms \rightarrow inclusion of 8 new patients (Step 2B)

Note: if a large number of patients stopped the treatment for at least 8 consecutive days, the hypothesis will be that the ointment form is not well accepted. Then we consider it is worthwhile to check this point by including 8 additionnal patients.

If there is an imbalance between arms (difference > 1), (unblinded data will be transmitted to DSMB):

- The number of “stops” is higher in the placebo arm
 - If “0” or “1” patients in active arm stop treatment \rightarrow inclusion of 16 new patients (**Step 2A**)
 - If “2” patients in active arm stop treatment \rightarrow inclusion of 8 new patients (**Step 2B**)
- The number of “stops” is higher in the active arm
 - If difference between arms is 2 \rightarrow inclusion of 8 new patients (**Step 2B**)
 - If difference between arms is over 2 \rightarrow inclusions may be discontinued (**Step 2C**).

The first 8 patients will be included in the Lyon center. Further inclusions will take place in all centers.

For the following steps, we consider the total number of patients who have a cessation of treatment for at least 8 consecutive days for safety concerns. Indeed, if 50% or more of patients are “in failure”, the continuation of the study may be called into question and the analysis on the main judgement criteria will then not be relevant.

- **STEP2 – Following inclusions, all centers**

STEP 2A- In case of inclusion of 16 new patients.

For these 16 patients, on day 31 (phone call): information regarding adverse events (AE), severe adverse events (SAE) and observance of the treatment for the first 30 days of treatment are collected. Additionally, safety assessment is carried out on the data collected at the visit after the end of treatment for the first 8 patients.

Based on these data, a DSMB meeting (#2) will be consulted and will give its recommendations on the continuation of the study according to the following theoretical equations:

- If less than 12 of the 24 patients stop treatment for 8 consecutive days due to safety concerns, 24 new patients will be included (**Step 3A**). Total number of patients included: $8 + 16 + 24 = 48$.
- If 12 or more patients stop treatment for at least 8 consecutive days due to safety concerns, depending on the group imbalance, the DSMB may request the lifting of the blind and inclusions may be discontinued (**Step 3B**). Total number of patients included: $8 + 16 = 24$.

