4.3.2 Secondary judgement criteria

1. Adverse Events (AE) and Severe Adverse Events (SAE) observed throughout the study (clinical examination, epistaxis grids, ENT examination at each visit before and after the treatment). Additionally, all patients are contacted by phone after 15 and 30 days of treatment in order to collect data on tolerance and observance of the treatment.
2. Clinical efficacy criteria:
 - Nosebleed duration will be evaluated by the nosebleed monitoring grids completed by the patient (Appendix 1), collected at inclusion (V1): observation of the nosebleeds in the 6 weeks prior to inclusion, at the end of the treatment (V2): observation of the nosebleeds in the 6 weeks during treatment, and at the end of the study (V3): observation of the nosebleeds in the 6 weeks after the end of the treatment.
 - Progress in the number of nosebleeds. This criterion will be evaluated by the nosebleed monitoring grids completed by the patient (Appendix 1) collected at inclusion (V1): observation of the nosebleeds in the 6 weeks prior to inclusion, at the end of the treatment (V2): observation of the nosebleeds in the 6 weeks during treatment, and at the end of the study (V3): observation of the nosebleeds in the 6 weeks after the end of the treatment.
 - Comparison of the number of red blood cell transfusions between inclusion (V1) (collected over 6 weeks before treatment), the end of the treatment (V2) (collected over 6 weeks of treatment) and at the end of the study (V3) (collected over 6 weeks after the end of the treatment).
 - Progress in the scores obtained in the SF36 quality of life questionnaire

completed at inclusion (V1), at the end of the treatment (V2) and at the end of the study (V3).

- Progress in the ESS (Epistaxis Severity Score) using data from the specific questionnaire (Appendix 2) completed at inclusion (V1), at the end of the treatment (V2) and at the end of the study (V3).

Biological efficacy criteria: progress in hemoglobin and serum ferritin concentrations between inclusion (V1) and the end of the treatment (V2) and at the end of the study (V3).

3. Systemic absorption, after 1, 3 and 6 weeks of nasal administration, will be evaluated by a tacrolimus dosage in the blood at the end of the treatment.

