6.7 Synopsis of the study per patient

	Inclusion V1 J0	Blood sample D8 (to 10)	Phone Call D15 (to 18)	Blood sample D22 (to 24)	Phone Call D31 (to 37)	V2 D43 (to 50)	V3 D85 (to 100)
Inclusion / exclusion criteria	x						
Epistaxis grids surrender	x		x		x	x	
Epistaxis grids collection	x					x	x
Consent Form signature	x						
Pregnancy Test	x						
Clinical examination (HR, BP)	x					x	x
ENT examination	x					x	x
Hémoglobinemia, serum ferritin	x					x	x
FK 506 dosage		x		x		x	
Treatment : protopic/placebo dispensation	x						
Product return						x	
Blood Cell transfusions collection	x					x	x
ESS questionnaire	x					x	x
SF36 Quality of life questionnaire	x					x	x
Concomitant treatment collection	x		x		x	x	x
Adverse events collection	x		x		x	x	x

Legend: D = day V = visit

Table 1: Synopsis of the study per patient

7 Intercurrent events

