7.1.2 Serious adverse event (SAE)

A **serious adverse event** (SAE) is any untoward medical occurrence that at any dose:

- Results in death
- Is life-threatening (*the term "life-threatening" in the definition of "serious" refers to an event in which the patient was at risk of death at the time of the event ; it does not refer to an event which hypothetically might have caused death if it were more severe*)
- Requires in-patient hospitalization or prolongation of existing hospitalization
- Results in persistent or significant disability/incapacity
- Is a congenital anomaly/birth defect
- Is a medically significant event:

Medical and scientific judgment should be exercised in deciding whether expedited reporting is appropriate in situations, such as important medical events that may not be immediately life-threatening or result in death or hospitalization but may jeopardize the patient or may require intervention to prevent one of the outcomes listed in the definition above.

The term "severe" is a measure of intensity, thus a severe adverse event is not necessarily serious. For example, "nausea of several hours" duration may be severe but may not be clinically serious.

For "TACRO" study, any tacrolimus blood concentration resulting > 5ng/ml and any sign of infection under treatment should be considered as medically significant event and reported immediately by the investigator to the sponsor as a SAE.

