9.2.1 Analysis populations

9.2.1.1 “Efficacy” population in intention to treat

This population will be composed of all the randomized patients. If patients stop the study treatment, their follow-up will be maintained in order to obtain the epistaxis grids.

9.2.1.2 “Efficacy” population per protocol

This population will be composed of all the patients who have received all the treatments set out in the protocol. A treatment will be considered complete if the patient received at least a total of 60 administrations out of 84 (twice a day for 42 days) envisaged by the protocol.

9.2.1.3 “Safety” population

This population will be composed of all the patients who have received at least one ointment.

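### The 6-week tacrolimus sample may be drawn up to Day 50, about 7.5 days after dosing ends, which biases that one time point toward no absorption

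*Combined protocol and SAP*

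**What the plan says.** - **Objective.** The synopsis lists systemic absorption after 1, 3 and 6 weeks of nasal use as a secondary objective. Sections 2.2, 6.1 and 7.4.4 schedule blood levels on Days 8, 22 and 43.
- **Dosing.** Section 9.2.1.2 counts a course as complete with "at least a total of 60 administrations out of 84 (twice a day for 42 days", so the planned course is 84 applications over 42 days.
- **Third sample.** Section 6.5 is headed "Visit at the end of the treatment, V2 = at day 43 (up to day 50 tolerated", and its list of procedures includes "A blood sample is collected (4 mL on EDTA) for tacrolimus dosage". Table 1 (section 6.7) puts the level in the V2 column, with the same tolerance to Day 50.
- **Other two samples.** Table 1 gives each a 2-day window during treatment: Day 8 to 10, and "Blood sample D22 (to 24".
- **Evaluation.** Section 4.3.2 says that absorption after 1, 3 and 6 weeks "will be evaluated by a tacrolimus dosage in the blood at the end of the treatment". Section 9.2.2.5 reports the percentage of patients with absorption and lists detected levels. It does not say which sample counts, what limit defines detection, or how time since the last dose is treated.
- **Half-life.** Section 1.3.4, on repeated skin application, states that "the average half-life of tacrolimus was estimated to be 75 hours for adults".
- **Use of the level for safety.** Section 7.1.2 makes "any tacrolimus blood concentration resulting > 5ng/ml" reportable as an SAE. Under sections 2.2 and 7.4.4, treatment stops from 5 ng/mL and the patient is hospitalized above 20 ng/mL.

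**The concern.** The two early samples are taken while the patient is still applying the ointment. The third is taken after the last planned dose, and its window runs for a further week off treatment. Nothing in the protocol asks the patient to continue until a late V2, and nothing limits the interval between last dose and sample. The 6-week result therefore mixes patients sampled about half a day after dosing with patients who may have been off the drug for more than a week.

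The error has one direction, because a later sample can only read lower. At stake is the only measurement of exposure after the full course, in what the protocol describes as a route of unknown safety (section 2.2). A diluted reading also passes unnoticed: under section 4.3.2 results are withheld during the study unless they exceed 5 ng/mL.

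**Working it through.** **Inputs**
- Half-life 75 h (section 1.3.4, adults, skin). The documents give no nasal half-life, so half and double this value are also shown.
- 84 applications, twice daily for 42 days (section 9.2.1.2): 2 × 42 = 84, which reproduces the plan's figure.
- Day 15 is 14 days after the start (section 6.3), so Day 1 is the first dosing day and the last planned dose falls on the evening of Day 42.
- Sample assumed to be taken in the morning, with first-order decline.

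**Formula.** Fraction of the end-of-treatment level remaining = 2^(−h/half-life), where h is hours since the last dose.

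| Sample day | h | 37.5 h | 75 h | 150 h |
|---|---|---|---|---|
| Day 43 | 12 | 80% | 90% | 95% |
| Day 45 | 60 | 33% | 57% | 76% |
| Day 50 | 180 | 4% | 19% | 44% |

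At 75 h the three values are 2^(−0.16) = 0.895, 2^(−0.8) = 0.574 and 2^(−2.4) = 0.189. If the course starts in the evening and the last dose falls on the morning of Day 43, the Day 50 interval is 168 h and 21% remains.

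**Cross-check.** Summing 84 doses given every 12 h with the same half-life puts the Day 50 level at 21% of the Day 43 level. This agrees with 0.189/0.895 = 0.21.

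**Effect on the 5 and 20 ng/mL rules, Day 50, 75 h**
- A true 5 ng/mL reads 5 × 0.189 = 0.95 ng/mL.
- A true 20 ng/mL reads 20 × 0.189 = 3.8 ng/mL.
- To read 5 ng/mL, the level at the last dose must be 5/0.1895 = 26 ng/mL (24 ng/mL if the last dose is on the morning of Day 43).
- For half-lives of 150 h and 37.5 h that level is 5/0.435 = 11 and 5/0.0359 = 139 ng/mL.

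**Effect on detection.** This trial's assay limit is not in the documents. Taking the 0.025 ng/mL quoted in section 1.3.4 for infant skin studies as an illustration, the lowest end-of-treatment level still detectable is 0.025/0.895 = 0.028 ng/mL on Day 43 and 0.025/0.1895 = 0.13 ng/mL on Day 50.

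**What the earlier samples cover.** Share of steady state reached = 1 − 2^(−h/75): Day 8, 1 − 2^(−168/75) = 79%; Day 22, 1 − 2^(−504/75) = 99%. With constant absorption, Day 22 already shows almost the full level.

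**The case against.** The case for leaving the plan alone is substantial, and most of it stands.

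- **Day 50 is the edge of a tolerance.** The sample is scheduled for Day 43, where about 90% remains. The documents do not give the share of late visits. This limits the size of the problem but does not remove it.
- **The safety consequence is small.** Day 22 is close to steady state, so a later rise would require absorption itself to increase. Section 1.3.4 reports, for infants' skin, falling exposure as lesions healed and no accumulation. By V2 there is no dosing left to stop. At the second DSMB meeting "safety assessment is carried out on the data collected at the visit after the end of treatment for the first 8 patients", but the numerical continuation rules there count treatment interruptions, not blood levels.
- **Detection is more robust than the thresholds.** In the illustration above, only end-of-treatment levels between about 0.03 and 0.13 ng/mL change from detected to undetected.

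Three stronger readings are tempting, and the documents do not support them.

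- A reader might infer from 4.3.2 that absorption is judged on the V2 sample alone, so that a patient stopped for a high Day 8 level would count as not absorbing. The same sentence names weeks 1, 3 and 6, and the synopsis, sections 2.2, 6.1 and 7.4.4 and Table 1 all plan three samples. A Day 8 level above 5 ng/mL would be an SAE, and section 9.2.2.5 lists any detected level. The wording of 4.3.2 is loose, but it does not make V2 decisive.
- A reader might infer that the time of the last application is unknown. The daily grid has morning and evening boxes (section 6.2, Appendix 1) and is collected at V2, so date and half-day can be derived. That is precise enough against a 75 h half-life. What is missing is any instruction to use it.
- A reader might call this a calculation error. No figure in the documents is wrong; the issue is the width of a sampling window.

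**Conclusion.** The point holds as a minor one with a cheap remedy. The 6-week absorption result can be biased toward no absorption by up to about 80% of the level at the edge of the window (19% remaining; 4% to 44% across half-lives of 37.5 to 150 h), and a level well above 5 ng/mL can go unreported. The Day 8 and Day 22 samples are sound and would catch sustained high exposure, so what is lost is the 6-week time point and any rise after Day 22.

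This rests on three assumptions: dosing stops after 42 days as written, decline is first-order, and the skin half-life is a fair guide to nasal use. How many patients would be affected cannot be determined from the documents.

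**What to change.** 1. **Window (6.5 and Table 1).** Give the third sample its own window, separate from V2: Day 41 to 43, on treatment or within about 12 hours of the last dose. Draw it at the local laboratory, adding a line to the prescription already issued at V1 for Days 8 and 22, or at V2 if V2 is on Day 43. At a minimum, cap it at Day 45 to match the other 2-day windows; about 57% then remains. Keep Day 50 for the rest of V2.
2. **Interval.** Derive the time since the last application from the existing grid boxes and list it beside each level.
3. **Wording.** In 4.3.2, name Day 8, Day 22 and end of treatment as the sampling times instead of end of treatment alone. In 9.2.2.5, report the percentage detected by day and at any of the three samples.

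**Cost.** A separate local draw for patients whose V2 is not on Day 43, with no extra assay and no change to the blinding procedure or the 5 and 20 ng/mL rules. A visit that slips at short notice may miss Day 41 to 43, which is why the Day 45 cap is useful as a fallback. Continuing the ointment until a late V2 would also close the gap, but it would exceed the 6 weeks that section 2.2 gives as the longest recommended treatment period.
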